4. STUDY DESIGN

4.1. Overall Design

This is a Phase I, first-time-in-human (FTIH), randomized, double-blind (sponsor unblinded), single-center, placebo-controlled, dose-escalation study to determine the safety, tolerability, and pharmacokinetic (PK) profile of GSK3342830 after administration of single (Part 1) and repeat (Part 2) IV doses in healthy adult subjects, and after administration of a single IV dose in healthy adult Japanese subjects (Part 3). Part 1 will investigate escalating single IV doses of GSK3342830. Part 2 will investigate escalating repeat IV doses of GSK3342830 with repeat dosing for 14 days and multiple dosing per day for 13 days as follows: a single IV infusion on Day 1, TID IV infusions on Days 2 through 14 (approximately every 8 hours), and a single IV infusion on Day 15. Part 3 will investigate a single IV dose of GSK3342830 in Japanese subjects.

For Parts 1 and 2, on Day 1, before study drug administration, subjects who meet the criteria for study entry will be assigned to the current dose level cohort and randomized to receive GSK3342830 or placebo. For Part 3, on Day 1, before study drug administration, subjects who meet the criteria for study entry will be randomized to receive GSK3342830 or placebo. All doses of GSK3342830 or placebo are planned to be administered as a 1-hour infusion.

This is the first administration of GSK3342830 in humans; therefore, the study design may change based on emerging data from each cohort. As preliminary safety, tolerability,

and PK results are reviewed internally at GSK and with the clinical study site, the following adjustments may be made to the proposed study design:

- The proposed dose levels, dosing frequency, infusion duration, and/or infusion volume of GSK3342830 may be adjusted during the course of Part 1 and/or Part 2 of the study.
- The duration of repeat dose administration planned for Part 2 may be adjusted.
- Cohorts may be added to or removed from either study Part 1 or Part 2 depending on findings from previous cohorts.
- Pharmacokinetic sampling and/or study assessment schedules may be changed.

This study will aim to explore the safety, tolerability, and pharmacokinetics of a wide range of exposures in healthy adult subjects. The exposures observed in animal toxicology studies will be used to guide dose escalation. Systemic exposures as measured by AUC in the human subjects in this study may exceed the systemic no observed adverse effect level (NOAEL) animal exposures from 4-week GLP toxicology studies as long as the doses administered in the study are safe and well tolerated. This approach is based on the following considerations:

- In the 4-week GLP studies, there was no dose-limiting organ toxicity in the animals (rats and monkeys) with exposures up to 2000 mg/kg/day, the highest dose tested.
- This study will incorporate a risk mitigation strategy (see Section 4.6.1).
- In the 4-week GLP studies, all observed systemic findings in the animals were mild to moderate and readily monitored in the clinic.
- Bayesian predictive probabilities of area under the concentration-time curve (AUC) from time zero to 24 hours after dosing (AUC[0-24]) and maximum plasma concentration (C_{max}) meeting criteria defined in Section 9.3.2, along with safety data will be used to drive decision making for dose escalation. The dose will be escalated only if it is supported by the safety, tolerability, and preliminary PK results from the preceding dose levels in the study.
- The planned maximum duration of repeat dosing in the study is 14 days.

As the efficacious exposure levels of GSK3342830 are uncertain, this approach provides the best chance of success in reaching therapeutic levels and establishing a sufficient margin of safety.

Planned C_{max} exposures in humans will not exceed the C_{max} exposure of the NOAEL as determined by the preclinical safety studies.

The repeat dose escalation component (Part 2) of this study is planned to be initiated after completion and evaluation of all single dose cohorts up to and including 4000 mg. Initiation of Part 2 will be based on the evaluation of preliminary safety, tolerability, and PK data from the single dose escalation (Part 1) cohorts once safety at an exposure that

exceeds the daily exposure predicted for the Part 2 planned starting dose of 1000 mg TID is demonstrated, which is predicted to occur at the 4000 mg single dose.

The single dose administration in Japanese subjects component (Part 3) of this study is planned to be conducted in parallel with Part 2. The dose for the Part 3 cohort will be based on preliminary safety and tolerability results of doses determined to be safe and well tolerated in subjects of non-Japanese heritage after completion of the single escalation dose cohorts (Part 1).

The relationship between dose and plasma GSK3342830 exposure will be determined as part of dose escalation as described in Section 9.3.2.

4.2. Treatment Arms and Duration

[figure not shown]
Part 1: Single Dose Escalation in Healthy Adult Subjects

Part 1 is planned to include 6 dose level cohorts. Additional doses (1 per cohort) may be evaluated to further understand the study drug. The planned starting GSK3342830 dose in Part 1 is 250 mg administered as a single IV infusion. The dose is planned to increase in subsequent cohorts to 500, 1000, 2000, 4000, and ≤ 6000 mg IV as shown in Figure 1. Doses >6000 mg may be administered if the predicted C_{max} exposures will not exceed the NOAEL.

On Day 1, before study drug administration, subjects will be randomized to treatment with either GSK3342830 or placebo in a 3:1 ratio. As a safety precaution, all Part 1 cohorts will be split into 2 sub-cohorts for sentinel dosing. In each cohort, the first 2 subjects will receive either GSK3342830 or placebo (1 active/1 placebo). Dosing in the remaining 6 subjects (5 active/1 placebo) in that cohort will occur at least 24 hours later based on the safety results from the first sub-cohort. Study assessments will be performed as indicated in the Time and Events Tables (Section 7.1).

Doses are planned to escalate in a sequential fashion contingent on the safety, tolerability, and PK profile of approximately 4 subjects who received active treatment in the previous cohort. The evaluated subjects should be followed for a minimum of 48 hours after dosing. Dose escalations or reductions will progress with modifications based on the preliminary safety, tolerability, and PK data from the preceding cohorts.

Figure 1 Part 1 Single Dose Escalation Study Design Schematic

Note: Figure shows illustration of the planned doses, which may be switched, changed, or cancelled based on preliminary safety, tolerability, and pharmacokinetic data from preceding cohorts.

The AUC from time zero to the last quantifiable concentration after dosing (AUC[0-t]) and C_{max} observed in the human subjects in this study at each single dose will be compared with the systemic NOAEL animal exposure values in order to determine the magnitude of dose escalation.

The dose escalation strategy is based on the following 2 principles:

- Bigger dose escalation steps will be allowed at lower systemic exposures as the expected risk of AEs at these exposures is low. The magnitude of dose escalation steps will be progressively restricted at higher exposures.
- Once a certain dose is reached, the magnitude of dose escalation steps will be restricted regardless of systemic exposure.

The following algorithm will be used for dose escalation in Part 1:

For each dose level, the human AUC and C_{max} values after a single dose will be calculated as percentage of the NOAEL animal exposures. The next dose level will then be determined as described in [Table 1](#).

Table 1 Single Dose Escalation Scheme

Human exposure at current dose as percentage of rat NOAEL	Dose escalation to next dose will be no higher than	Predicted human exposure at next dose as percentage of NOAEL will be no higher than ^{1,2}
≤2%	10-fold	N/A
>2 and ≤5%	8-fold	30%
>5 and ≤15%	6-fold	60%
>15 and ≤30%	4-fold	90%
>30%	3-fold	N/A

N/A = not applicable, NOAEL = no observed adverse effect level.

NOTES:

1. The relationship between dose and plasma GSK3342830 exposure, and associated variability will be characterized by a power model once data are available from 3 dose levels. Prior to that, prediction of the human exposure at the next dose will be based on population pharmacokinetic (PK) modeling (if feasible) or on the assumption of dose-exposure proportionality. If prior PK results show less than proportional increase in exposure with increasing dose, the prediction will be based on the assumption that the fold exposure increase to fold dose increase ratio will be the same with the current dose escalation as it was with the previous one. If prior PK results show more than proportional increase in exposure with dose, subsequent dose escalations will not be higher than 3-fold.
2. Human exposure may exceed the NOAEL exposures based on acceptable safety and tolerability data. Initial exposure targets will be based on NOAEL exposures.

Both conditions (dose escalation to the next dose level and predicted human exposure at next dose as percentage of NOAEL) will be met when determining a dose escalation step based on [Table 1](#) (i.e., the condition allowing a smaller dose escalation step will limit the maximum dose escalation).

- Once the dose is ≥500 mg, any further dose escalation will be no higher than 3-fold irrespective of the observed exposures.
- The targeted mean AUC and C_{max} in Part 1 are NOAEL exposures for AUC(0-24) (2875 h•µg/mL) and C_{max} (2270 µg/mL). Human exposure may

exceed the NOAEL exposures based on acceptable safety and tolerability data. Initial exposure targets will be based on NOAEL exposures.

In Part 1, subjects will remain confined to the clinical unit from admission on Day –1 until all scheduled safety and PK assessments have been completed on Day 3. The duration of study (from Screening to the Follow-up visit) for each subject will be up to approximately 43 days.

[figure not shown]
Part 2: Repeat Dose Escalation in Healthy Subjects

Part 2 is planned to include a sequential panel of up to 3 dose level cohorts. Additional repeat dose cohorts may be evaluated to further assess the safety, tolerability, and pharmacokinetics of GSK3342830. The planned starting GSK3342830 dose in Part 2 is 1000 mg administered as a single IV infusion on Day 1, TID IV infusions on Days 2, 3, 4, 5, 6, 7, 8, 9, 10, 11, 12, 13, and 14, and a single IV infusion on Day 15. The dose is planned to increase in subsequent cohorts to 2000 and 4000 mg TID as shown in [Figure 2](#). The starting dose and maximum dose may be changed based on clinical safety and PK findings in Part 1 or earlier doses in Part 2 and consideration of the AUC(0-24) and Cmax exposures based on the NOAEL.

On Day 1, before study drug administration, subjects will be randomized to treatment with either GSK3342830 or placebo in a 4:1 ratio. Study assessments will be performed as indicated in the Time and Events Tables (Section 7.1).

Doses are planned to escalate in a sequential fashion based on the preliminary safety, tolerability, and PK data from Part 1 and at least 14 days of repeat dosing in approximately 5 subjects who received active treatment in the previous cohort in Part 2. The evaluated subjects should be followed for a minimum of 24 hours after dosing on Day 15. The dosing frequency, duration of dosing, and decision to dose in the next dose level may be changed based on the safety, tolerability, or PK findings in Part 1 or earlier doses in Part 2.

Figure 2 Part 2 Repeat Dose Escalation Study Design Schematic

Note: Figure shows illustration of the planned doses, which may be switched, changed, or cancelled based on preliminary safety, tolerability, and pharmacokinetic data from preceding cohorts.

The following rules will guide dose selection in Part 2:

- The starting daily dose in Part 2 will be selected such that its predicted AUC(0-24) and C_{max} on the last day of dosing (i.e., account for any drug accumulation) is no higher than the exposure of a dose that has been found to be safe and well tolerated in Part 1.
- Subsequent doses in Part 2 may be selected using the previously described criteria for the Part 2 starting dose. Alternatively, a dose may be selected even if it does not meet these criteria provided it is no more than 4-fold higher than a previous dose that has been found to be safe and well tolerated upon repeat dosing in Part 2.
- The targeted mean AUC(0-24) and C_{max} in Part 2 are the NOAEL exposures (AUC[0-24] of 2875 h•µg/mL and C_{max} of 2270 µg/mL). Human exposure may exceed the NOAEL animal exposures based on acceptable safety and tolerability data. Initial exposure targets will be based on NOAEL exposures.

In Part 2, subjects will remain confined to the clinical unit from admission on Day –1 until after all scheduled safety assessments have been completed on Day 16. The duration of study (from Screening to the Follow-up visit) for each subject will be up to approximately 56 days.

Part 3: Single Dose in Healthy Adult Japanese Subjects

Part 3 is planned to include 1 cohort (Cohort J). The planned GSK3342830 dose in Part 3 will be either 250, 500, 1000, 2000, 4000, or ≤6000 mg based on preliminary safety and tolerability results of doses determined to be safe and well tolerated in subjects of non-Japanese heritage after completion of the single escalation dose cohorts (Part 1). The dose in Part 3 will be administered as a single IV infusion on Day 1.

On Day 1, before study drug administration, subjects will be randomized to treatment with either GSK3342830 or placebo in a 4:1 ratio. Study assessments will be performed as indicated in the Time and Events Tables (Section 7.1).

In Part 3, subjects will remain confined to the clinical unit from admission on Day –1 until all scheduled safety and PK assessments have been completed on Day 3. The duration of study (from Screening to the Follow-up visit) for each subject will be up to approximately 43 days.

4.3. Type and Number of Subjects

For Part 1, approximately 48 healthy adult subjects will be enrolled with approximately 8 subjects in each of the 6 planned cohorts. In each Part 1 cohort, approximately 6 subjects will be assigned to active treatment and approximately 2 subjects will be assigned to placebo. For Part 2, approximately 30 healthy adult subjects will be enrolled with approximately 10 subjects in each of the 3 planned cohorts. For Part 3, approximately 10 healthy adult Japanese subjects will be enrolled. In each Part 2 cohort and the Part 3 cohort, approximately 8 subjects will be randomized to receive active treatment and approximately 2 subjects will be randomized to receive placebo.

Additional subjects/cohorts may be enrolled to allow for evaluation of additional dose levels.

Decisions regarding replacement of subjects prematurely discontinued from study drug in any cohort will be made by the investigator and the GSK medical monitor on a case-by-case basis. Subjects may only be randomized to one cohort and may only participate in one part of the study.

4.4. Design Justification

The design of this FTIH study is consistent with global regulatory guidelines for protocol design including subject selection, estimation of starting dose, precautions that are applied within and between dosing cohorts, dose escalation scheme, risk mitigation, and stopping rules [EMA, 2007 and DHHS, 2005].

Scheduled assessments of subjective symptoms, and objective clinical laboratory tests, vital signs, and 12-lead electrocardiograms (ECGs) will be obtained to monitor subject safety. In order to further mitigate the risks to subjects who participate in this study, subjects will be specifically monitored for findings observed in animal species with GSK3342830, findings identified with similar catechol cephalosporin compounds, as well as known risks common to cephalosporin antibiotics. These potential risks and their mitigations are presented in Section 4.6.1.

Part 2 of this study is planned to include 14 days of repeat dosing based on the following 2 factors:

- An objective of this study is to establish the safety and tolerability of the medication for a dosing duration that will be clinically relevant in future efficacy studies of acute bacterial infection. Most acute bacterial infections for which GSK3342830 may be developed will need to permit up to 14 days of treatment.
- Non-adverse hematologic changes were observed in the 4-week preclinical safety studies after 14 days of dosing. In this FTIH study, 14 days of dosing will provide additional reassurance of hematologic safety specifically for future subjects with acute bacterial infection requiring up to 14 days of therapy.

4.5. Dose Justification

Dose selection of GSK3342830 for this FTIH study was based on NOAEL data from animal toxicology studies, predicted pharmacokinetics for humans using PK data from preclinical species, and a targeted therapeutic exposure based on efficacy data from a rat pneumonia model. GSK3342830 is a catechol cephalosporin antibiotic that utilizes the bacterial iron transport system to facilitate transport into bacteria and disrupts the synthesis of the peptidoglycan layer of bacterial cell walls. This is not a human target; therefore, the minimum anticipated biological effect level in humans for GSK3342830 was not determined.

As described in the following sub-sections,

- While the maximum recommended starting dose is 1935 mg, the proposed starting dose is 250 mg, which is predicted to have AUC(0-t) and C_{max} values 45-fold and 83-fold lower than the NOAEL values, respectively.
- The predicted dose to achieve the therapeutic exposure target ranges from 500 to 2000 mg, which is predicted to have AUC(0-t) values 5.6- to 22-fold lower and C_{max} values 10- to 42-fold lower than the NOAEL values after administration of single doses, and AUC(0-24) values 1.9- to 7.5-fold lower and C_{max} values 10- to 42-fold lower than the NOAEL values after administration of repeat doses.
- The anticipated maximum 6000 mg single dose will provide an AUC exposure of 1933 h•µg/mL (predicted AUC encompassing 95% of the simulated population) with a safety margin of 1.48-fold and a C_{max} of 849 µg/mL (predicted C_{max} encompassing 95% of the simulated population) with a safety margin of 2.67-fold.
- The anticipated maximum 4000 mg TID dose will provide an AUC exposure of 3846 h•µg/mL (predicted AUC[0-24] encompassing 95% of the simulated population) that may exceed the systemic NOAEL AUC(0-24) exposure of 2875 h•µg/mL (safety margin of 0.93-fold) and a C_{max} of 569 µg/mL (predicted C_{max} encompassing 95% of the simulated population) with a safety margin of 3.98-fold.
- Based on a concentration limitation of 25 mg/mL, IV solution volumes between 100 to 250 mL would support single doses of 2500 to 6000 mg (IV formulation work is ongoing. Formulation instructions will be available in the Pharmacy Manual before the start of the study).
- Importantly, dose escalation decisions will be based on observed exposure, safety, and tolerability data for GSK3342830 from the previous dose level.

Data Used for Dose Justification

No observed adverse effect level (NOAEL)

The primary AEs in the 4-week GLP toxicology studies were those at the infusion site. The NOAEL dose in both the rat and monkey for these local infusion site effects (ulcer, perivascular/vascular inflammation, thrombus) was 500 mg/kg; the formulation concentration at this dose was 25 mg/mL for rats and 50 mg/mL for monkeys. These local effects were considered secondary to the high concentrations and resultant high osmolalities of the formulations at doses higher than 500 mg/kg/day. The concentration of the clinical formulation will be limited to no greater than 25 mg/mL (the concentrations at the NOAEL dose for rats), which should preclude these local irritation effects. Based on a concentration limitation of 25 mg/mL, IV solution volumes between 100 to 250 mL would support single doses of 2500 to 6000 mg (IV formulation work is ongoing. Formulation instructions will be available in the Pharmacy Manual before the start of the study) as shown in [Table 2](#).

Table 2 Single IV Infusion Doses, Concentrations, and Osmolality¹

Dose (mg)	Concentration (mg/mL) for a 100 mL infusion	Concentration (mg/mL) for a 250 mL infusion	Final osmolality ² (mOsm/kg)
250	2.5		302
500	5		314
1000	10		339
2000	20		388
4000		16	388
6000		24	407

NOTES:
1. Theoretically calculated osmolality values.
2. Based on 100 mL (250 to 2000 mg doses) and 250 mL (4000 and 6000 mg doses) infusion volumes.

Given that the infusion site reactions can be addressed by formulation, the 2000 mg/kg dose and exposures were selected to define the exposure limits. Slight decreases (10 to 20%) in red blood cell count, hemoglobin, and hematocrit, accompanied by an increase in reticulocytes, as well as other clinical pathology changes considered non-adverse were observed at 2000 mg/kg/day in male and female monkeys; these were considered secondary to the severe and ongoing inflammation induced by the infusion site effects. The hematological findings showed evidence of reversibility by week 4 of dose administration and showed recovery by 4 weeks post dosing. In summary, the hematologic findings were mild, reversible, and able to be monitored in the clinic. The NOAELs of 2000 mg/kg in the rat and monkey with NOAEL exposures of 2875 h•µg/mL (rat) and 2270 µg/mL (monkey) for AUC(0-t) and C_{max}, respectively, were selected to define the exposure limits.

Scaling to human exposure

GSK3342830 is structurally similar to another catechol cephalosporin compound with generally comparable *in vivo* PK profiles in preclinical species. Scaling using the dedrick monkey method was proven to accurately predict the human clearance and volume of distribution for the former compound (observed values within 20% of predicted values). Thus, the dedrick method, along with a single-point allometry method, was selected to predict human clearance and volume of distribution for GSK3342830. Both methods showed similar predicted human clearance values of approximately 0.82 mL/min/kg (single-point allometry) and 0.93 mL/min/kg (dedrick monkey), while predicted volume of distribution was 0.121 L/kg (dedrick monkey).

In vivo efficacy models

A major objective of this study is to establish safety across a clinically relevant dose range to enable a future Phase II efficacy study. *In vivo* efficacy models predict target therapeutic AUC(0-t) exposures of 112 to 467 h•µg/mL after administration of single doses and AUC(0-24) values of 336 to 1401 h•µg/mL after TID dose administration. Scaling of animal exposure to humans predicts GSK3342830 will achieve these exposures at doses between 500 to 2000 mg. Additional details on the *in vivo* efficacy calculations and animal to human scaling is available in [Appendix 9](#).

Maximum Recommended Starting Dose

The systemic NOAEL dose level of 2000 mg/kg in the rat (most sensitive species) was converted to the human equivalent dose based on body surface area using the US Food and Drug Administration (FDA) Guidance for estimation of the maximum safe starting dose [DHHS, 2005]. After applying an uncertainty safety factor of 10 (the guideline default) to the human equivalent dose, the maximum recommended starting dose is 1935 mg.

- The proposed starting dose is 250 mg which is predicted to have AUC(0-t) and Cmax values 45-fold and 83-fold lower than the NOAEL values, respectively.
- Assuming an IV solution volume between 100 to 250 mL, the drug concentration of 1 to 2.5 mg/mL is well below the lower concentration limitation of 25 mg/mL.

Dose Predicted to Achieve the Therapeutic Exposure Target

Doses of 500 to 2000 mg are predicted to achieve the target therapeutic exposure (total AUC[0-t] values of 112 to 467 h•µg/mL after administration of single doses and AUC[0-24] values of 336 to 1401 h•µg/mL after administration of repeat TID doses). Comparisons of the therapeutic doses with the NOAELs from the 2000 mg/kg exposures suggest the following safety margins:

- AUC(0-t) values 5.6- to 22-fold lower and Cmax values 10- to 42-fold lower than the NOAEL values after administration of single doses.
- AUC(0-24) values 1.9- to 7.5-fold lower and Cmax values 10- to 42-fold lower than the NOAEL values after administration of repeat doses.

Predicted Maximum Dose Exposure Margins: Single Dose Escalation Cohorts

Based on the systemic NOAEL AUC(0-24) exposure of 2875 h•µg/mL and Cmax exposure of 2270 µg/mL, the anticipated maximum 6000 mg single dose will provide:

- An AUC exposure of 1933 h•µg/mL (predicted AUC encompassing 95% of the simulated population [Table 8, Appendix 9]) with a safety margin of 1.48-fold.
- A Cmax of 849 µg/mL (predicted Cmax encompassing 95% of the simulated population [Table 8, Appendix 9]) with a safety margin of 2.67-fold.

Predicted Maximum Dose Exposure Margins: Repeat Dose Escalation Cohorts

Given the evolving PK and pharmacodynamic data currently being generated through *in vivo* preclinical models, doses above 2000 mg TID may be required to adequately treat certain challenging bacteria in the clinic. With this in mind, the tolerability of repeat doses up to 4000 mg TID will be tested. Based on the systemic NOAEL AUC(0-24) exposure of 2875 h•µg/mL and Cmax exposure of 2270 µg/mL, the anticipated 4000 mg TID dose will provide:

- An AUC exposure of 3846 h•µg/mL (predicted AUC[0-24] encompassing 95% of the simulated population [[Table 9](#), [Appendix 9](#)]) that may exceed the systemic NOAEL AUC(0-24) exposure of 2875 h•µg/mL.
 - As described previously, dose escalation would be predicated on safety and PK data observed at the preceding dose (2000 mg TID) administered for 14 days with at least 24 hours post-dose observation.
- A Cmax of 569 µg/mL (predicted Cmax encompassing 95% of the simulated population [[Table 9](#), [Appendix 9](#)]) with a safety margin of 3.98-fold.

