 Systemic NOAEL exposures: AUC(0-24) = 2875 h•µg/mL and C_{max} = 2270 µg/mL.
 Target therapeutic exposure range for AUC(0-∞) is 112 to 467 h•µg/mL.
 Data given as median and percentile range (range for 90% of the simulated individual data values).

Table 9 Predicted Exposure Values After Administration of Repeat Doses

Dose (mg) TID	AUC(0-24) h•µg/mL			Cmax µg/mL		
	5 th percentile	50 th percentile	95 th percentile	5 th percentile	50 th percentile	95 th percentile
500	309	385	483	42.2	54.4	71.1
1000	618	777	960	84.8	110	143
2000	1227	1536	1920	168	218	286
4000	2460	3078	3846	334	437	569

[figure not shown]
NOTES:
Systemic NOAEL exposures: AUC(0-24) = 2875 h•µg/mL and Cmax = 2270 µg/mL.
Target therapeutic exposure range for AUC(0-24) is 336 to 1401 h•µg/mL.
Data given as median and percentile range (range for 90% of the simulated individual data values).
Repeat dose data were not simulated but are based on the single dose simulation.

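### Protocol 4.5 gives a 0.93-fold AUC safety margin beside the 95th-percentile exposure at 4000 mg TID; the ratio for that exposure is 0.75, and 0.93 matches the median

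*Protocol*

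**What the plan says.** The summary bullets of Protocol Section 4.5 give exposure margins for the highest planned doses.

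- **4000 mg TID, AUC.** "The anticipated maximum 4000 mg TID dose will provide an AUC exposure of 3846 h•µg/mL (predicted AUC[0-24] encompassing 95% of the simulated population". The sentence then says that this could be above the NOAEL AUC(0-24) of 2875 h•µg/mL and gives a "safety margin of 0.93-fold".
- **4000 mg TID, Cmax.** The same sentence gives 569 µg/mL, also on the 95% basis, "with a safety margin of 3.98-fold".
- **6000 mg single dose.** The preceding bullet gives an AUC of 1933 h•µg/mL on the same 95% basis, "with a safety margin of 1.48-fold", and a Cmax of 849 µg/mL with a margin of 2.67.

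The exposures come from Appendix 9. The 4000 mg row of Table 9 reads "4000 2460 3078 3846 334 437 569": the 5th, 50th and 95th percentiles of AUC(0-24), then the same percentiles of Cmax. The table note confirms the layout ("Data given as median and percentile range").

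The later sub-section of 4.5 on repeat-dose margins repeats 3846 against 2875 but gives no numerical AUC margin. The change list in Appendix 13 records no change to Section 4.5.

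**The concern.** A margin printed beside an exposure should be the ratio for that exposure. Here the exposure is an upper percentile, but the margin fits the median. A reader who takes the sentence at face value will think the upper-tail exposure is only slightly above the NOAEL.

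The regimen makes this matter. In Tables 8 and 9, 4000 mg TID is the only planned regimen with a predicted AUC above 2875. The next highest 95th percentiles are 1933 (6000 mg single dose) and 1920 (2000 mg TID). The subjects are healthy volunteers with no expected benefit (Section 4.6.2), and 0.93 is the protocol's only numerical AUC margin for this regimen.

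**Working it through.** **Inputs.** NOAEL: AUC(0-24) 2875 h•µg/mL and Cmax 2270 µg/mL (Section 4.5; notes to Tables 8 and 9). Predicted exposures: Tables 8 and 9. Margin = NOAEL exposure / predicted human exposure.

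**Step 1: try to reproduce 0.93 for AUC at 4000 mg TID.**

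| Basis | Calculation | Result |
|---|---|---|
| 95th percentile (the exposure in the sentence) | 2875/3846 | 0.748 |
| Median | 2875/3078 | 0.934 |
| 5th percentile | 2875/2460 | 1.169 |
| 95th percentile against the individual maximum of 3460 (Section 9.3.2) | 3460/3846 | 0.900 |

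Only the median gives 0.93.

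**Step 2: check the basis of the other maximum-dose margins.**

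| Margin | Printed | 95th percentile | Median |
|---|---|---|---|
| 6000 mg AUC | 1.48 | 2875/1933 = 1.487 | 2875/1545 = 1.861 |
| 6000 mg Cmax | 2.67 | 2270/849 = 2.674 | 2270/657 = 3.455 |
| 4000 mg TID Cmax | 3.98 | 2270/569 = 3.989 | 2270/437 = 5.195 |
| 4000 mg TID AUC | 0.93 | 2875/3846 = 0.748 | 2875/3078 = 0.934 |

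The first three agree with the 95th percentile (1.48 and 3.98 appear truncated rather than rounded) and are far from the median. The fourth is the reverse. Truncation would give 0.74, so it does not explain 0.93.

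**Step 3: check whether the median is used elsewhere in 4.5.** It is, for the lower doses:

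- 250 mg: 2875/64.3 = 44.7 (printed 45) and 2270/27.5 = 82.5 (83).
- 500 to 2000 mg single dose, AUC: 2875/128 = 22.5 (22) and 2875/512 = 5.62 (5.6).
- 500 to 2000 mg, Cmax: 2270/54.4 = 41.7 (42) and 2270/218 = 10.4 (10).
- 500 to 2000 mg TID, AUC: 2875/385 = 7.47 (7.5) and 2875/1536 = 1.87 (1.9).

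None of these is printed beside a 95th-percentile exposure. The 4000 mg TID AUC margin is the only one that pairs the two bases.

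**Step 4: size of the excess over the NOAEL.** At the 95th percentile, 3846/2875 = 1.34, or 34% above. At the median, 3078/2875 = 1.07, or 7% above.

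**The case against.** The best defence is that nothing depends on the figure. The sentence prints both 3846 and 2875 and says the NOAEL may be exceeded. Sections 4.1, 4.2 and 5.4.8 also allow exposure above the NOAEL. Going to 4000 mg TID depends on observed safety and PK at 2000 mg TID. All of this stands, and it limits the consequence. It does not make 0.93 the ratio of the two numbers beside it.

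A second argument is that the median may be the more relevant basis. The Part 2 rules in Section 4.2 target a mean AUC(0-24) of 2875, and Section 9.3.2 compares the mean with 2875 and an individual with 3460. This is a good reason to keep 0.93 in the text with a label, and so to prefer printing both margins. It does not justify an unlabelled 0.93 next to a 95th-percentile exposure. On the individual reference of 3460, the 95th percentile still lies above it: 3846/3460 = 1.11.

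Two qualifications also stand. The protocol does not say how 0.93 was obtained; the median is inferred from the exact match. And the Table 9 values were not simulated directly but scaled from single doses (3 × 1282 = 3846; 3 × 1026 = 3078), so the 34% and 7% are predictions on that basis.

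**Conclusion.** The concern holds. For the exposure printed, the AUC margin at 4000 mg TID is 0.75, not 0.93, so the sentence understates the predicted upper-tail excess over the NOAEL: 34%, against the 7% that goes with the median. The arithmetic uses only the protocol's own NOAEL and Table 9 values and needs no outside assumption. It should be corrected because it is a stated safety margin, wrong in the favourable direction, for the one regimen predicted to exceed the AUC NOAEL. It does not call the dose, the escalation rules or the analysis into question.

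**What to change.** In the 4000 mg TID bullet of Protocol Section 4.5, either replace 0.93 with 0.75 or print both margins with their basis: 0.93 at the median AUC(0-24) of 3078 and 0.75 at the 95th percentile of 3846. The second is preferable, because it keeps the central figure that relates to the mean-based target and also shows the upper-tail margin.

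The cost is one corrected or labelled figure in one bullet. Design, dose rules and analyses stay as they are; the stated margin becomes less favourable.
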